4.9 Discontinuation of Study Treatment, Withdrawal, and Compliance

Discontinuation from the study does not mean discontinuation from any clinically guided medical care. Subjects will be monitored for AEs/SAEs during the 4 week infusion testing period so long as an infusion took place.

In the absence of delays due to adverse events, study activities may continue until:

- Disease progression or instability as determined by the principal investigator.
- General or specific changes in the subject's condition renders the subject unacceptable for further treatment in the investigator's judgment.
- Intercurrent illness that prevents further participation.
- Subject decides to withdraw from the study.
- The subject has significant noncompliance with the protocol (defined as greater than 3 missed appointments).
- Unacceptable adverse event(s)
- Study stopping rules are met.

Subjects who sign the informed consent form, and are enrolled and receive the study intervention, but subsequently withdraw, or are withdrawn or discontinued from the study, will not be replaced.

Consent Withdrawal

A subject may decide to withdraw from the study at any time. UNC will follow its IRB of record's SOPs regarding consent withdrawal.

If a subject intends on withdrawing consent, staff should confirm which of the following options the subject chooses and document the discussion:

- Full consent withdrawal with no study follow-up.

- Selective consent withdrawal from interventional portion of the study, but agree to continued follow-up of associated clinical outcome information (i.e. study diary and/or blood draws).

Investigator-initiated Withdrawal

The investigator will withdraw a subject whenever continued participation is no longer in the subject's best interests. Reasons for withdrawing a subject include, but are not limited to, disease progression or instability, the occurrence of an severe adverse event or a concurrent illness, a subject's request to end participation, a subject's noncompliance or simply significant uncertainty on the part of the investigator that continued participation is prudent. The reason for study withdrawal and the date the subject was removed from the study must be documented.

4.10 Lost to Follow-up

The following actions must be taken if a participant fails to return to the clinic for a required study visit and/or is unable to be reached for follow-up:

- The investigator or designee must make every effort to regain contact and/or reschedule a missed visit with the participant.
- A participant is deemed lost to follow-up if his/her status cannot be obtained after *all* of the following occurs at two consecutive scheduled protocol calendar timepoints:
 - Three telephone calls (at least one day apart) from the study team are unanswered AND
 - A letter to the participant's last known mailing address goes unanswered AND
 - These contact attempts must be documented in the participant's study file.
- Update the EDC when a participant is officially considered lost to follow-up.
- If a subject is considered lost to follow-up, but subsequently contacts the participating site study team, the subject should be considered in follow-up again.

4.11 Accrual Suspension and Closure

The UNC PI facilitates the suspension and closing of accrual in the following manner:

- EDC tracks accrual throughout the study.
- If the study must be suspended, EDC and Clinical trial management software (ie Velos) is updated to a 'suspended' status.
- When the accrual number is reached, PI notifies staff of study closure.

4.12 End of Study Definition

A participant is considered to have completed the study if he or she has completed all phases of the study including the last visit or the last scheduled procedure shown in the calendar of events or has been discontinued.

4.13 Study Discontinuation and Closure

This study may be temporarily suspended or prematurely terminated if there is sufficient reasonable cause (as determined by the study principal investigator, DSMC, sponsor, and/or IRB). Written notification, documenting the reason for study suspension or termination, will be provided by the suspending or terminating party to study participants, investigator, funding agency, and regulatory authorities. If the study is prematurely terminated or suspended, the principal investigator (PI) will promptly inform the MCW Institutional Review Board (IRB) and sponsor and will provide the reason(s) for the termination or suspension. Study participants will be contacted, as applicable, and be informed of changes.

5 STUDY PLAN

5.1 RBC Unit Administration

Treatment will be administered on an outpatient basis. The study RBC unit will be administered per hospital protocol by the UNC RN staff per normal administration protocols. Subject vital signs will be taken at regular intervals per hospital protocol. The study staff will aseptically remove 50 ml (~4 tablespoons) of the same crossmatch-compatible RBCs into a syringe, and members of the Nuclear Medicine Department will label that sample with a radioisotope (⁵¹Chromium) per standard protocols. A portion of that tagged aliquot will be transferred into a

syringe to be infused into the subject. A second portion from that sample, pre chromium labeling, will be saved for future "omics" studies. The UNC *Nuclear Medicine department* study staff will be specifically responsible for the preparation and infusion of the chromium-labeled aliquot to the patient. The RN staff will be responsible for the transfusion of the non-labeled compatible red cell unit and lab blood draws.

5.2 Monitoring Subject Compliance

Pain and infection diary: The diary is adapted from previously published SCD studies.⁸⁷ Pain and infection symptoms will also be documented daily for 4 weeks along with the type, duration, and dose of antibiotics, if applicable. Daily, participants will rate pain on a numeric pain rating ordinal scale (0-10), indicate whether the pain was consistent with a "crisis," indicate whether they utilized a healthcare facility, and record the amount of opioids used. Infection symptoms will also be documented daily along with the type, duration, and dose of antibiotics, if applicable.

5.3 Follow-up Period

Patients will be followed for up to 28 days following their last study-related blood transfusion. Patients will not be followed after completion of the study protocol.

Patients removed from the study treatment for unacceptable SAEs will be followed until resolution or stabilization of the adverse event. SAEs will be followed until completion.

6 DOSING DELAYS/DOSE MODIFICATIONS

6.1 Monitoring and Toxicity Management

Each patient receiving G6PD-deficient and G6PD-normal RBCs will be evaluated for safety. The safety parameters include all laboratory tests and hematological abnormalities, physical findings and spontaneous reports of adverse events reported to the investigator by patients, and are outside laboratory values and clinical events considered usual for SCD.

The chromium agent used for red cell labeling has no known or previously reported risks of adverse events. Consequently, general tracking of adverse events will be conducted as noted in the following sections.

Each patient will be assessed periodically for any toxicity development. Toxicity will be assessed according to the CTCAE v 4.0.

We will specifically monitor for evidence of red cell hemolysis as a result of the red cell transfusion. Evidence of hemolysis will be obtain from clinical symptoms (fever, chills) and laboratory values obtained per study protocol (LDH, haptoglobin, and hemoglobin values).

Acute toxicity will be managed according to the symptoms and determined etiology. Most adverse events from transfusion can be managed symptomatically by standard over-the-counter medications, such as Tylenol for fevers, or Benadryl for allergic symptoms. Further management will depend upon the judgment of the clinician and may include ED admission or inpatient hospitalization.

Patients will also be monitored for exacerbations of the subjects underlying sickle cell disease: Vaso-occlusive pain crises, acute chest crises, stroke, serious infection, and priapism. This will be monitored by review of the patients electronic medical record, subject verbal report, and/or review of the daily diary.

7 ADVERSE EVENTS: DEFINITIONS AND REPORTING REQUIREMENTS

7.1 Definitions

1) Vaso-occlusive pain crisis: an episode of acute pain with no cause other than a vasoocclusive event lasting at least 24 hours that requires the administration of oral or parenteral opioids in a medical facility.

2) Acute Chest Syndrome: an acute illness requiring medical facility attention characterized by fever and/or respiratory symptoms, accompanied by a new pulmonary infiltrate on a chest X-ray.

3) Priapism: an acute illness requiring medical facility attention characterized by *an* erect penis that does not return to its flaccid state, despite the absence of both physical and psychological stimulation, within four hours.

4) Acute infection: an acute illness requiring medical facility intervention (i.e prescription of antibiotics or hospital admission) characterized by any subjective symptom.

5) *Chronic transfusion*: receiving red cell units on a 4-8 week schedule as part of routine, non-acute care).

6) Acute transfusion: receiving red cell units on an unscheduled basis to resolve an acute issue.

7.1.1 Adverse Event (AE) and Serious Adverse Events (SAE)

The investigator and his or her team will follow UNC policies related to adverse event reporting. This information may be found on the Human Research Protection Program website.

Serious AE (SAE) means any untoward medical occurrence that at any dose:

- **Death.** Results in death.
- Life threatening. Is life threatening (refers to an AE in which the patient was at risk of death at the time of the event. It does not refer to an event which hypothetically might have caused death if it were more severe).
- **Hospitalization**. Requires inpatient hospitalization or prolongation of an existing hospitalization (see clarification in the paragraph below on planned hospitalizations).
- **Disability/incapacity**. Results in persistent or significant disability or incapacity. (Disability is defined as a substantial disruption of a person's ability to conduct normal life functions).
- **Medically important event**. This refers to an AE that may not result in death, be immediately life threatening, or require hospitalization, but may be considered serious when, based on appropriate medical judgment, may jeopardize the patient, require medical or surgical intervention to prevent one of the outcomes listed above, or involves suspected transmission via a medicinal product of an infectious agent. Examples of such

medical events include allergic bronchospasm requiring intensive treatment in an emergency room or at home, blood dyscrasias or convulsions that do not result in inpatient hospitalization, or the development of drug dependency or drug abuse; any organism, virus, or infectious particle (e.g., prion protein transmitting transmissible spongiform encephalopathy), pathogenic or nonpathogenic, is considered an infectious agent.

Clarification should be made between a serious AE (SAE) and an AE that is considered severe in intensity (Grade 3 or 4), because the terms serious and severe are NOT synonymous. The general term severe is often used to describe the intensity (severity) of a specific event; the event itself, however, may be of relatively minor medical significance (such as a Grade 3 headache). This is NOT the same as serious, which is based on patient/event outcome or action criteria described above, and is usually associated with events that pose a threat to a patient's life or ability to function. A severe AE (Grade 3 or 4) does not necessarily need to be considered serious. For example, a white blood cell count of 1000/mm³ to less than 2000 is considered Grade 3 (severe) but may not be considered serious. Seriousness (not intensity) serves as a guide for defining regulatory reporting obligations.

7.1.2 Unanticipated Problem Involving Risk to Subject or Other

The investigator and his or her team will follow UNC policies related to unanticipated problems involving risks to subjects or others. This information may be found on the Human Research Protection Program website.

7.1.3 AE Attribution and Grading

Adverse	Event	Grading
---------	-------	---------

Grade	Description
0	No AE (or within normal limits).
1	Mild; asymptomatic or mild symptoms; clinical or diagnostic observations only; intervention not indicated.
2	Moderate; minimal, local or noninvasive intervention (e.g., packing cautery) indicated; limiting age-appropriate instrumental activities of daily living (ADL).
3	Severe or medically significant but not immediately life- threatening; hospitalization or prolongation of hospitalization indicated; disabling; limiting self-care ADL.
4	Life-threatening consequences; urgent intervention indicated.
5	Death related to AE.

Adverse Event Attribution

Attribution is an assessment of the relationship between the AE and the medical intervention.

Relationship	Attribution	Description
Unrelated to investigational agent/intervention	Unrelated	The AE is clearly NOT related to the intervention
	Unlikely	The AE is doubtfully related to the intervention
Related to investigational agent/intervention	Possible	The AE may be related to the intervention
	Probable	The AE is likely related to the intervention
	Definite	The AE is clearly related to the intervention

Relationship Assessment: In-Depth Definitions

For all collected AEs, the clinician who examines and evaluates the subject will determine the adverse event's causality based on temporal relationship and his/her clinical judgment. The degree of certainty about causality will be graded using the categories below:

Definitely Related: There is clear evidence to suggest a causal relationship, and other possible contributing factors can be ruled out. The clinical event, including an abnormal laboratory test result, occurs in a plausible time relationship to drug administration and cannot be explained by concurrent disease or other drugs or chemicals. The response to withdrawal of the drug (dechallenge) should be clinically plausible. The event must be pharmacologically or phenomenologically definitive, with use of a satisfactory rechallenge procedure if necessary.

Probably Related: There is evidence to suggest a causal relationship, and the influence of other factors is unlikely. The clinical event, including an abnormal laboratory test result, occurs within a reasonable time sequence to administration of the drug, is unlikely to be attributed to concurrent disease or other drugs or chemicals, and follows a clinically reasonable response on withdrawal (dechallenge). Rechallenge information is not required to fulfill this definition.

Possibly Related: There is some evidence to suggest a causal relationship (e.g., the event occurred within a reasonable time after administration of the trial medication). However, the influence of other factors may have contributed to the event (e.g., the subject's clinical condition, other concomitant events). Although an adverse drug event may rate only as "possibly related" soon after discovery, it can be flagged as requiring more information and later be upgraded to "probably related" or "definitely related," as appropriate.

Unlikely: A clinical event, including an abnormal laboratory test result, whose temporal relationship to drug administration makes a causal relationship improbable (e.g., the event did not occur within a reasonable time after administration of the trial medication) and in which other drugs or chemicals or underlying disease provides plausible explanations (e.g., the subject's clinical condition, other concomitant treatments).

Unrelated: The AE is completely independent of study drug administration, and/or evidence exists that the event is definitely related to another etiology. There must be an alternative, definitive etiology documented by the clinician.

7.2 Known AEs List

Below are know AE's related to blood cell transfusion. Many of these risks are common to sickle cell disease and are known to occur. Reporting of these instances will be based on frequency and severity under the determination of trained study staff.

- Myocardial infarction
- Pulmonary embolism
- Stroke
- Renal failure
- Sepsis
- Ventricular tachycardia
- Ventricular fibrillation
- Red cell hemolysis (immune and non-immune)
- Transfusion-associated congestive heart failure/transfusion-associated circulatory overload (TACO)
- Transfusion-related acute lung injury (TRALI)
- Anaphylaxis
- Graft vs. Host Disease (GVHD)
- Grade 2 or higher events of the following types:
 - Allergic reaction
 - Sinus bradycardia
 - o Sinus tachycardia
 - o Hypertension
 - \circ Hypotension
 - o **Dyspnea**
 - o Hypoxia
 - o Wheezing
 - o Cough
 - Fever
 - o Chills
 - Hemolysis
 - o Hyperkalemia
 - o Hypocalcemia
 - o Hyperbilirubinemia
 - Hemoglobinuria.

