7.4.3 Routine Reporting Procedures for AEs

Study staff must report the Adverse Event form within 7 days of each study transfusion. The Adverse Event Checklist will indicate whether or not one or more of the events listed in Section 8.2 occurred during the transfusion. The PI will be also be notified of the identified event within 24 hours of learning of the event by phone or email.

Since this is an investigator-initiated study, the principal investigator, also referred to as the sponsor-investigator, is responsible for reporting serious adverse events (SAEs) to any regulatory agency and to the sponsor-investigator's IRB. Regardless of expectedness or causality, all SAEs (including serious pretreatment events) must also be reported to the DSMB as soon as possible, but no later than five calendar days after the sponsor-investigator's observation or awareness of the event.

Signs or symptoms reported as adverse events will be graded and recorded by the investigator, according to the CTCAE. When possible, signs and symptoms indicating a common underlying pathology should be noted as one comprehensive event.

The investigator will assess all adverse events and determine reporting requirements to the UNC Safety Monitoring Committee (SMC) and MCW's Institutional Review Board. The investigator will report SAEs to any required regulatory agency and to the sponsor-investigator's IRB.

All adverse events, whether or not unexpected, and whether or not considered to be associated with the use of the study drug, will be entered into the studies AE log.

Reporting to the Safety Monitoring Committee

Regardless of expectedness or causality, all SAEs (including serious pretreatment events) must also be reported to the SMC as soon as possible, but no later than five calendar days of the sponsor-investigator's observation or awareness of the event.

Report Method: The investigator will use email to report SAEs to the SMC. The SAE report must include event term(s), serious criteria and the sponsor-investigator's or sub-investigator's determination of both the intensity of the event(s) and the relationship of the event(s) to study drug administration. Intensity for each SAE, including any lab abnormalities, will be determined by using the NCI CTCAE as a guideline whenever possible.

Reporting to MCW Committee Institutional Review Board

The principal investigator must report events to the MCW IRB within five business days of his/her awareness of the event.

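### Sections 7.2 and 6.1 conflict with the log-everything rule in 7.4.3, so capture of non-serious events could differ by regimen; the attribution grades also presuppose a treatment that can be withdrawn

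*Combined protocol and SAP*

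**What the plan says.** **Reporting.** After introducing the known transfusion events, Section 7.2 states: "Reporting of these instances will be based on frequency and severity under the determination of trained study staff". Hemolysis is on the list twice, once without a grade and once among the events that count from Grade 2 upward. Section 7.4.3 sets a different rule: "All adverse events, whether or not unexpected, and whether or not considered to be associated with the use of the study drug" are to be entered in the study's AE log.

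**Scope of safety parameters.** Section 6.1 counts all laboratory tests, hematological abnormalities, physical findings and spontaneous reports, then adds that these "are outside laboratory values and clinical events considered usual for SCD". It does not define usual. The same section also says "We will specifically monitor for evidence of red cell hemolysis as a result of the red cell transfusion" and "Patients will also be monitored for exacerbations of the subjects underlying sickle cell disease".

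**Checklist.** The Adverse Event Checklist in Section 7.4.3 asks whether a listed event occurred during the transfusion, and it points to Section 8.2 for the list. The list is in 7.2. Section 7.3 runs AE capture from the pre-transfusion sample to the week 4 visit, in both periods.

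**Attribution.** Section 7.1.3 defines a probably related event as one that, among other joined conditions, "follows a clinically reasonable response on withdrawal (dechallenge". For definitely related it says: "The response to withdrawal of the drug (dechallenge) should be clinically plausible", with rechallenge if necessary. Section 3.1 gives one experimental unit per period.

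**The concern.** Excess hemolysis after G6PD-deficient units is the hazard that motivates the trial, and hemolysis is also part of the background in sickle cell disease. If staff may decide which listed events to report, and if findings usual for the disease can be set aside, a non-serious hemolytic event could be recorded for one participant and omitted for another.

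The blinding makes this more than a matter of tidiness. Section 4.8 gives clinical staff who oversee participation, collect data and enter them access to the unit's G6PD status. It argues that unblinding does no harm because the key components are objective. A discretionary decision to report is not objective. Section 11.3 presents safety results to the Safety Monitoring Committee (SMC) by RBC unit group, so a threshold that shifts with knowledge of the unit would show up as a difference between regimens, or would hide one.

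The attribution wording raises a separate problem: it was written for a drug that can be stopped.

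**Working it through.** The point rests on wording, so the check sets the rules side by side.

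1. *Which rule governs recording?* Section 7.2 gives discretion over listed events, and 7.4.3 gives none over any AE. No sentence ranks them. The 7.2 sentence might concern only onward reporting, but it does not say so.

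2. *Does the log rule settle it?* Not fully. The log can hold only what has first been called an AE. Under Section 7.4 a laboratory change becomes an AE when the investigator considers it clinically relevant, and 6.1 tells that investigator to look outside what is usual for the disease. Section 6.1 promises hemolysis monitoring by symptoms, LDH, haptoglobin and hemoglobin, but defines no event.

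3. *Does the checklist settle it?* No. It covers the transfusion, while capture runs to week 4, and its section reference is wrong.

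4. *Can capture differ by regimen?* Yes, through the staff access in Section 4.8. The documents do not show that it would.

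5. *What is outside the problem?*
   - All serious adverse events go to the SMC within five calendar days whatever their expectedness or cause (7.4.3).
   - Grade 4 and 5 events must be reported to the SMC (11.3).
   - Haptoglobin, LDH, bilirubin, cell-free hemoglobin and reticulocytes are drawn on schedule and compared between regimens as outcomes (schedule of procedures, 9.1.1, 9.6).

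6. *Attribution.* One unit per period cannot be withdrawn after it has been given. For probable, the withdrawal response is joined to the other conditions by an and, so read literally the grade cannot be met. For definite, the text says only that the response should be plausible, and rechallenge is conditional. Possible carries no such condition, is classed as related in the 7.1.3 table, and is enough to trigger notice of a serious event to the SMC chair (11.3).

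**Illustration only.** The documents give no event or reporting rates. Let *p* be an assumed risk of a non-serious event per participant under one regimen and *r* an assumed fraction reported. With 16 independent participants, the chance that at least one event is reported is 1 − (1 − *pr*)^16.

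| *p* | *r* = 100% | 75% | 50% | 25% |
|---|---|---|---|---|
| 5% | 0.560 | 0.457 | 0.333 | 0.182 |
| 10% | 0.815 | 0.713 | 0.560 | 0.333 |
| 20% | 0.972 | 0.926 | 0.815 | 0.560 |

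For example, *p* = 10% and *r* = 50% gives 1 − 0.95^16 = 0.560. In a trial of this size, whether an event type appears at all can depend on reporting. The table does not estimate the loss.

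**The case against.** The strongest reply is that hemolysis is measured, not left to reporting. The laboratory markers are scheduled, listed as outcomes and analyzed by regimen, so excess hemolysis reaches the analysis whatever staff record as an AE. This stands. A reader might infer that the safety rules as a whole screen out the effect under study; the documents do not support that.

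A reader might also infer that every event on the 7.2 list is discretionary. That goes too far: any listed event that is serious, or is Grade 4 or 5, must be reported. Nor does 6.1 simply remove sickle cell events, because it requires monitoring for pain crisis, acute chest crisis, stroke, serious infection and priapism.

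The SMC reviews all adverse events at its yearly call and receives each participant's AE log. The items it is specifically asked to determine are mostly serious or unexpected events. This limits the harm but does not remove it, because the yearly review sees only what was logged.

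On attribution, 7.1.3 also says causality rests on timing and clinical judgment, and its table has no withdrawal condition. A reader might infer that the wording blocks a related rating or delays escalation. It does neither, since possible suffices for both, and the safety analysis in 9.8 states no attribution filter.

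**Conclusion.** The concern holds as a conflict between stated rules. Sections 7.2 and 6.1 allow judgment where 7.4.3 allows none, and staff who can know the regimen exercise that judgment. The consequence is possible uneven capture of non-serious events in summaries by unit group. Its direction and size cannot be derived from the documents, and it rests on two conditions: that staff follow 7.2 as written, and that knowledge of G6PD status influences what they report. The primary recovery endpoint, serious-event reporting and the hemolysis laboratory outcomes are untouched.

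The attribution wording is a separate and smaller defect. It can push a grade down from probable or definite to possible, and no rule in the protocol was found that treats those grades differently. Both should be corrected because the correction is nearly free.

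**What to change.** - Reconcile 7.2 and 6.1 with 7.4.3: every listed event is recorded with grade and date through week 4 in both periods, whether or not it is considered usual for sickle cell disease. Limit any discretion to onward expedited reporting of non-serious events. State whether the two hemolysis entries differ.
- Extend the checklist to the capture window in 7.3 and correct its reference to 7.2.
- In 7.1.3, replace the withdrawal and rechallenge wording with criteria usable for a single infusion: timing, laboratory evidence and alternative causes.
- In 9.8, state that safety tables are by regimen received.

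Change from the pre-transfusion laboratory value should not serve as the only yardstick. That sample is taken before the whole exchange, and the study unit is the last unit given (4.8), so the change mixes the effect of the exchange with that of the unit.

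The cost is protocol wording and additional AE log lines. No new visits, samples or procedures are needed.
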